### 12.2.5. Severity (Intensity)

For AEs that are quantifiable (e.g. blood pressure, lab assessments), the Investigator will assess the severity (intensity) of all AEs according to the following grading system:

- Grade 1 – (Mild AE) - event does not require medical intervention
- Grade 2 – (Moderate AE) - event is treatable with standard medical intervention
- Grade 3 – (Severe AE) - event requires intensive medical intervention

## 12.3. Reporting Adverse Events

All new events, as well as those that worsen in intensity or frequency relative to baseline, which occur must be captured. The Investigator or his/her staff should elicit information regarding the occurrence of adverse events through physical examination results, review of laboratory results, and, if appropriate, questioning of the neonate's parents/guardians.

Information to be recorded for each AE includes:

- A medical diagnosis of the event (if a medical diagnosis cannot be determined, a description of each sign or symptom characterizing the event should be recorded)
- The date and time of onset of the event
- The date and time of resolution of the event
- Assessments of severity, causal relationship, and seriousness of the AE (see definitions in [Sections 12.2.3, 12.2.4, and 12.2.5](#))
- Action(s) taken (if any) for management of the AE
- Outcome of the AE: subject recovered (without sequelae); subject recovered with sequelae; event ongoing; subject died

All AEs will be followed until resolution or stabilization.

### 12.3.1. Reporting Complications of Prematurity

Complications of prematurity will not be classified as AEs, but as study outcomes.

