### **6.3. Endpoints**

#### **6.3.1. Primary Endpoints**

The incidence and severity of AEs, SAEs and changes in clinical parameters in STP206-treated subjects compared to control subjects from baseline through 30 days after the last dose of blinded study treatment.

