#### **6.3.2. Secondary Endpoints**

The secondary endpoints of the study are:

- The incidence and the severity of AEs and SAEs in STP206-treated subjects compared to control subjects from baseline through six months after the last dose of blinded study treatment
- The incidence of clinical events (NEC, sepsis/bacteremia, feeding intolerance, death, morbidity/complications of prematurity) in STP206-treated subjects compared to control subjects from baseline through hospital discharge
- The assessment of the fecal shedding of STP206 organisms in STP206-treated subjects compared to its baseline and to control subjects through the last dose of blinded study treatment

- The assessment of the changes in routine clinical parameters in STP206-treated subjects compared to control subjects at baseline through the last dose of blinded study treatment
- The assessment of the progression of standard neonatal growth parameters in STP206-treated subjects compared to control subjects through the 6-month postdosing visit.

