### 10.3. Safety Procedures

#### 10.3.1. Physical Examination

Physical examinations will be performed that will include assessments of the following body systems:

- Head, Eyes, Ears, Nose, Throat (HEENT)
- Cardiovascular
- Respiratory
- Central nervous system
- Abdomen/Gastrointestinal
- Genitourinary
- Musculoskeletal
- Dermatologic/Skin

Physical examination findings will be noted in the subject medical records. The screening and Day 1 physical examinations will be recorded on a CRF for the subject. Subsequent physical examinations performed in the NICU will not be recorded on a CRF but all adverse findings meeting the definition of an AE (see [Section 12.2.1](#)), independent of relationship or severity, will be recorded on the CRF as either adverse events or complications of prematurity.

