### 10.3.5. Adverse Event Assessment

AEs occurring in neonates will be determined based upon physical findings, functional findings, laboratory findings, and routine observation of the neonate. AEs will be assessed from the time of initial administration of blinded study treatment through 6 months following completion of dosing and be recorded regardless of severity or relationship to blinded study treatment. Ongoing AEs will be followed by standard NICU practice until resolution or stabilization. For each AE, the following information will be recorded:

- Onset date and time
- Resolution date and time
- Severity/intensity (see [Section 12.2.5](#))
- Relationship to study drug (see [Section 12.2.4](#))
- Serious or non-serious (see [Section 12.2.3](#))
- Actions taken to manage/treat the event
- Outcome of the event - resolved, resolved with sequelae, ongoing, death

Complications of prematurity (see [Section 10.5.2](#)) will be recorded separately and not recorded as AEs.

---

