The incidence of sepsis with ██████████ is extremely rare and is NOT an anticipated event. Guidelines to the Investigator are provided in the study protocol for monitoring and documentation in the unlikely case the event occurs. Any sepsis occurring during the study is considered an SAE (*i.e.*, other important medical event; see [Section 12.2.3](#)) and will be reported as described in [Section 12](#) of study protocol.

If the central laboratory identifies ██████████ (STP11) or ██████████ (STP6) in the isolate provided from the local laboratory, the study enrollment will be halted and a DSMC meeting will be convened to review the case (see [Appendix E](#)).

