### 10.5.2.5. *Other Complications of Prematurity*

Study staff will evaluate neonates for the following other clinical events:

- Spontaneous gastrointestinal perforation
- Patent ductus arteriosus requiring treatment with indomethacin, ibuprofen or surgery
- Late onset sepsis
- Late onset Candida sepsis

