#### 12.2.3. Serious Adverse Event

A **serious adverse event** (SAE) is an AE that in the view of either the investigator or sponsor, results in any of the following outcomes:

- Results in death
- Is life-threatening (an event that in the view of either the investigator or sponsor, its occurrence places the patient or subject at immediate risk of death; it does not include an event that had it occurred in a more severe form, might have caused death)
- Requires in-patient hospitalization or prolongation of existing hospitalization

- Is a congenital anomaly or birth defect
- Results in persistent or significant disability/incapacity or substantial disruption of the ability to conduct normal life functions
- Is an important medical event  
An important medical event that may not be immediately life-threatening or result in death or hospitalization but based upon appropriate medical judgment, may jeopardize the patient or may require medical or surgical intervention to prevent one of the other outcomes listed above. Examples of such events are intensive treatment in an emergency room for allergic bronchospasm; blood dyscrasias or convulsions that do not result in hospitalization; or development of drug dependency or drug abuse.

The term “severe” is often used to describe the intensity (severity) of an event; the event itself may be of relatively minor medical significance (such as a severe headache). This is not the same as “serious”, which is based on subject/event outcome or action criteria usually associated with events that pose a threat to a subject’s life or functioning.

In addition to the above definitions of SAEs, all occurrences of confirmed bacteremia will also be considered an SAE (*i.e.*, other important medical event).

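### Late onset sepsis is both a complication that is not an AE and an SAE, with no stated exception; and no listed Safety-population table counts deaths from all causes

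*Protocol*

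**What the plan says.** **Complications.** Protocol 10.5.2.5 lists late onset sepsis and "Late onset Candida sepsis" among the other complications of prematurity. Section 10.3.5 says of the Section 10.5.2 complications that they "will be recorded separately and not recorded as AEs", and 12.3.1 repeats the rule: "Complications of prematurity will not be classified as AEs, but as study outcomes". For physical examination, 10.3.1 says that adverse findings meeting the AE definition "will be recorded on the CRF as either adverse events or complications of prematurity".

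**Sepsis.** Protocol 10.3.5.1 says: "Any sepsis occurring during the study is considered an SAE". Section 12.2.3 defines an SAE as a kind of AE and adds that "all occurrences of confirmed bacteremia will also be considered an SAE".

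**Windows.** The primary endpoint (6.3.1) covers AEs, SAEs and changes in clinical parameters "from baseline through 30 days after the last dose of blinded study treatment". A secondary endpoint (6.3.2) covers AEs and SAEs "from baseline through six months after the last dose of blinded study treatment". Death as a clinical event is a separate secondary endpoint and runs to hospital discharge.

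**Tables.** SAP 8.6.2.1 defines the mortality variable as inpatient death, and Tables 14.2.5.1 to 14.2.5.3 show it for the ITT population. Tables 14.3.2.3.1 to 14.3.2.3.3 show fatal TEAEs for the Safety population. Tables 14.2.3.1 to 14.2.3.3 show sepsis by arm for the ITT population.

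**The concern.** The primary endpoint is AE and SAE incidence after dosing premature infants with live organisms. Sepsis is among the events a safety reader will look for first. If one site files late onset sepsis as an SAE and another files it only as a complication, the SAE table does not mean the same thing at every site.

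Deaths raise a related point. The protocol chooses to treat NEC, perforation and the other complications as outcomes rather than AEs, and that choice is not disputed here. Its consequence is that the as-treated death tables, which are restricted to TEAEs, need not contain deaths from those complications. It is also unclear whether the first stopping criterion in Protocol 7.1.1, which concerns a related death due to an AE, reaches a death from a complication.

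**Working it through.** The documents give no figure to reproduce: Protocol 13.1 and SAP 4.5 say that the sample size has no statistical basis. The check is a side-by-side reading, followed by simple arithmetic for scale.

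**Step 1: sepsis**

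| Source | What follows for a late onset sepsis |
|---|---|
| Protocol 10.5.2.5 | It is a complication of prematurity |
| Protocol 10.3.5 and 12.3.1 | It is not recorded or classified as an AE |
| Protocol 10.3.5.1 | It is an SAE, reported under Section 12 |
| Protocol 12.2.3 | If bacteremia is confirmed, it is an SAE; every SAE is an AE |

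Rows 2 and 3 cannot both hold for one event. Section 10.3.5.1 refers the reader to Section 12, which contains 12.3.1. The bacteremia sentence does not settle every case, because 10.6.2 recognises clinical sepsis with negative cultures.

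**Step 2: listed death outputs (SAP 11)**

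| Output | Population | Limit |
|---|---|---|
| Tables 14.2.5.1 to 14.2.5.3 | ITT, as randomised | Inpatient deaths |
| Tables 14.3.2.3.1 to 14.3.2.3.3 | Safety, as received | Fatal TEAEs |
| Listing 16.2.7.4 | Safety | AEs with a fatal outcome |
| Tables 14.1.1.1.5 to 14.1.1.1.7 (end of study) | ITT, as randomised | Disposition; no 30-day cut |
| Listing 16.2.1.3 | None stated in its title | End-of-study disposition, by infant |

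None is an all-cause count on the Safety population over the 30-day and 6-month windows. Disposition may undercount deaths: Protocol 9.5 asks for one primary reason for withdrawal, and NEC of stage II or worse is itself a withdrawal criterion (9.5.1), although such infants are still followed (9.5.2).

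**Step 3: weight of one infant**

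Inputs are 8 groups of 12 infants randomised 2:1 (Protocol 7.1).

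- Planned total: 8 × 12 = 96. STP206: 8 × 8 = 64, that is 32 low dose and 32 high dose. Control: 8 × 4 = 32.
- Pooled column: 1/32 = 3.1 percentage points.
- Stratum column of 8: 1/8 = 12.5 points.
- Controls of one cohort: 1/4 = 25 points.
- If 110 are enrolled (Protocol 9.1) in the same proportions, a pooled column is 110/3 = 36.7 and one infant is 2.7 points.
- With all 20 centers active: 96/20 = 4.8 infants per center on average.

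**Step 4: whether complication deaths are a remote case**

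Protocol 5.1 gives NEC in about 10% of VLBW infants and about 20% mortality among those with NEC. The six groups at 1500 g or below hold 6 × 12 = 72 infants.

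- NEC death risk: 0.10 × 0.20 = 0.02.
- Expected NEC deaths: 72 × 0.02 = 1.44.
- Chance of at least one: 1 − 0.98^72 = 0.77.

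This assumes that the background rates apply to this trial and to both arms. It counts NEC deaths wherever they occur, and those in hospital would appear in the ITT mortality tables.

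**The case against.** **The specific sepsis rule is mandatory.** Section 10.3.5.1 gives a site no discretion, while 10.3.5 and 12.3.1 are general and do not name sepsis. The either/or wording in 10.3.1 concerns physical-examination findings. The objectives, endpoints and SAP list sepsis apart from other complications, and SAP 8.7.2 lists SAEs by system organ class and preferred term. On that reading sepsis enters the SAE tables. This stands as the better reading, so a claim that the plan leaves sepsis out of the SAE tables would go too far. What remains is that the exception is nowhere written.

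**Sepsis is already tabulated by arm.** Tables 14.2.3.1 to 14.2.3.3 do this, so the events are not lost. But those tables are ITT and are not tied to the AE/SAE tables, their population or their windows.

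**A reader might infer bias between arms.** The documents do not support that. Assessing staff are blinded (Protocol 7.5), so a site's recording habit can differ between arms only by chance. All comparisons are exploratory (Protocol 13.2.1, SAP 7.1).

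**A reader might infer that a mortality endpoint is missing, or that later deaths vanish.** Neither holds. Protocol 6.3.2 sets the death endpoint through discharge, and the mortality tables match it. The inpatient definition is not limited to the birth admission, so a death on readmission could count. Other deaths can be found through the disposition tables and listings. The DSMC sees primary and secondary endpoint data at each review (Protocol 7.7), and fatal NEC goes to FDA even when it is not an expedited report (12.4.1). The second stopping criterion, an STP206 organism from a sterile site, does not depend on an AE label. The gap is one of presentation on the safety population and windows.

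**The table shells and CRF are not available.** The point therefore rests on the SAP text and the listed table titles.

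**Conclusion.** The sepsis passages conflict as written. The text leans towards SAE but does not say so, and this leaves the sepsis part of the primary endpoint open to differences in site recording. The expected effect is noise and possible undercounting. Each infant recorded differently moves a pooled column by 3.1 points at planned size. How many would be affected cannot be estimated, because the documents give neither a sepsis rate nor a misrecording rate; the number is zero if every site applies 10.3.5.1.

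The death gap also holds on the listed outputs. Following 12.3.1 literally leaves NEC and other complication deaths out of the only Safety-population death tables, and nothing listed gives all-cause deaths by treatment received with a 30-day cut. ITT and as-treated counts differ only for undosed or misdosed infants, whose number is not given. The larger shortfalls are post-discharge deaths from complications and the missing 30-day cut. The number of deaths affected is unknown; the NEC illustration shows only that complication deaths are plausible at this size. Both defects are modest and cheap to correct.

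**What to change.** 1. **Protocol.** Reconcile 10.3.5, 10.5.2.5 and 12.3.1 with 10.3.5.1 and 12.2.3 so that sepsis is recorded one way. State how the first stopping criterion in 7.1.1 treats a death from a complication. The clinical rule is for the sponsor; this review does not choose it.
2. **SAP 8.7.2, deaths.** Add a Safety-population table of all-cause deaths by treatment received, through 30 days and through 6 months after the last dose, whatever the AE or complication label or the withdrawal reason. Add a footnote for sites that used a different 6-month reference, which SAP 8.7.2 says occurred.
3. **SAP 8.7.2, sepsis.** Beside the SAE table, show a sepsis/bacteremia count drawn from both the AE/SAE records and the sepsis/complication records, with each infant counted once. Reconcile it with Tables 14.2.3.1 to 14.2.3.3.

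**Cost.** One clarifying amendment and two extra tables, which SAP 11 allows. The tables assume that dates of death and last dose are held in the database. Serious-event counts may rise in both arms. An amendment cannot harmonise records already made, which is why the combined sepsis count is needed as well.

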## 12.4. Reporting Serious Adverse Events

All serious events, regardless of relationship to study drug, must be reported to Leadiant as described below.

- SAEs that are fatal or life-threatening must be reported to Leadiant or their designee by telephone *immediately* after site personnel first become aware of the event. Within 24 hours, the Leadiant Serious Adverse Event Form must be faxed to the medical monitor or designee regardless of whether full information regarding the event is known or not. If full information is not known, additional follow-up by the Investigator will be required.
- All other SAEs must be reported to the Leadiant medical monitor or designee within 24 hours by phone, e-mail or fax after becoming aware of the event. Within 48 hours, the Leadiant Serious Adverse Event Form must be faxed to the medical monitor or designee

regardless of whether full information regarding the event is known or not. If full information is not known, additional follow-up by the Investigator will be required.

All SAE reports will be reported to a representative of Leadiant as described in the Study Reference Manual.

All SAEs will be evaluated by the Leadiant medical monitor or designee. If meeting the requirements for expedited reporting, Leadiant will report the AE to all regulatory authorities with jurisdiction over ongoing trials with the study drug and to all other investigators involved in clinical trials with STP206.

The Investigator must report all SAEs, reported to regulatory authorities in an expedited manner to the reviewing IRB. For all other SAEs, the Investigator must report all SAEs in accordance with the requirements of the reviewing IRB.

#### 12.4.1. Reporting of Other Adverse Events of Special Interest

In addition to reporting of SAEs, the following AEs that do not meet serious criteria will be reported to Leadiant within 48-hours using the Leadiant Serious Adverse Event Form:

- Any discontinuation of study drug dosing due to a severe (i.e., Grade 3) AE. These AEs will be reported to FDA by Leadiant.
- Any infection confirmed to be due to [REDACTED] that is not reported as an SAE. Infections due to STP206 bacteria will be reported to the FDA by Leadiant.

In addition, per FDA's request during a teleconference held on 22 July 2014, blinded desk copies of all cases of NEC resulting in surgery or death that did not meet expedited reporting requirements to qualify as a 7- or 15-day IND safety report will be submitted to the FDA via a Clinical Information Amendment to the IND.

### 13. STATISTICS

#### 13.1. Sample Size Determination

The sample size for this study will not be determined statistically.

#### 13.2. Statistical Methodology

##### 13.2.1. General Analysis Considerations

All summaries and statistical analyses will be performed using SAS, Version 9.4 or higher. Descriptive summaries will consist of frequencies and percentages for categorical measures and of the number of subjects, mean, standard deviation, median, minimum, and maximum values for continuous measures. Descriptive summaries will be presented for each treatment group. Any statistical comparisons performed on the data will be done for exploratory analysis purposes only.

### 13.2.2. Analysis Populations

The safety population will be all randomized subjects who received at least one dose of blinded study drug. The Intent-to-treat (ITT) population will consist of all randomized subjects who received study medication and have at least one post-baseline evaluation.

### 13.2.3. Data Analysis

Details regarding the data analyses planned for the study will be outlined in the statistical analysis plan (SAP). Any changes to planned methods and analyses will be described and justified in the SAP, as appropriate. The SAP will be finalized prior to database lock.

#### *13.2.3.1. Efficacy Data Analysis*

The following efficacy parameters will be compared between those who received STP206 vs. control:

- Feeding intolerance
- Death
- NEC incidence
- Incidence of sepsis
- Incidence of other neonatal complications of prematurity (ROP, IVH, BDP, etc)

Details regarding the analysis of efficacy data will be provided in the SAP.

#### *13.2.3.2. Safety Data Analysis*

AEs will be assessed from the time the subject receives the initial dose of study drug through 6 months following the last dose. AEs will be coded according to Medical Dictionary for Regulatory Activities (MedDRA) and summarized in frequency tables displaying counts and percentages by body system, preferred term, and treatment group. Subjects reporting multiple events will only be counted once.

In addition, AEs will be summarized by relationship to study drug and by severity. For assessing relationship to study drug, any event with a study drug relationship marked as “possible”, “probable” or “definite/related” on the CRF will be considered related to study drug.

All SAEs will also be summarized in a frequency table.

Medical history (maternal, pregnancy and infant), concomitant medications, and physical examination findings, will also be summarized by treatment group at each timepoint where data was collected.

Information on method (bottle, breast, tube) and content of feedings (formula or breast milk) will be summarized.

#### *13.2.3.3. Pharmacokinetic Data Analysis*

None.

#### *13.2.3.4. Fecal Shedding Data Analysis*

Fecal shedding [REDACTED] for each treatment group will be assessed by quantitative and/or qualitative methods. Counts will be summarized as a continuous measure and will be summarized descriptively by treatment at each time point. Qualitative responses will be categorized and analyzed by counts and percentages and summarized by treatment at each time point.

In addition, change from baseline will be calculated and summarized descriptively by treatment to determine whether fecal shedding values return to baseline levels.

Duration of fecal shedding will be summarized descriptively by treatment group.

#### 13.2.4. Handling Missing, Repeated, Unused, and Spurious Data

It is not anticipated that there will be a need to adjust for missing data in this study. All data for this study will be analyzed as collected on the CRF. If the need arises to account for any special circumstances presented by the data, details of how it will be handled will be documented in the SAP.

#### 13.2.5. Reporting of Deviations to Statistical Methodology

Any deviations to the protocol defined analysis will be documented in the SAP. Deviations in analyses described in the SAP will be documented in the study report.

### **13.3. Interim Analysis**

An interim analysis is not planned.

### **13.4. Statistical Criteria for Termination of the Study**

There are no statistical criteria for stopping the study.

## **14. ADMINISTRATIVE**

### **14.1. Changes to Study Protocol**

#### 14.1.1. Protocol Amendments

Protocol changes must be in the form of a written amendment approved by Leadiant.

Protocol amendments and necessary revisions to the informed consent form must be submitted by the Investigator to the local IRB and such amendments will only be implemented after written approval of the requisite IRB. Protocol changes to eliminate an immediate hazard to a study subject may, at the direction of Leadiant, be implemented immediately by the Investigator. The Investigator must then immediately inform the IRB and obtain required approvals.

If a protocol amendment requires revision to the informed consent form, the revised IRB-approved form must be used to re-consent subjects currently enrolled in the study and the new form must be used to obtain consent from new subjects prior to enrollment.

All amendments will be submitted to local regulatory authorities by Leadiant as required by local regulation.

